### **9.2.5 Study Drug Exposure**

Study drug exposure will be summarized based on the Safety Set. Duration of study drug exposure (in days) will be calculated as [last dose date – first dose date + 1 day] within the TE period, regardless of any interruption in dosing between the first and the last dose. For subjects who enroll in another qualified Vertex study and resume participation in this study, time spent in the other study will be excluded.

Study drug exposure (in weeks) will be summarized descriptively by the number of subjects (n), mean, SD, median, min, and max. It will also be summarized by interval, using counts and percentages.

### **9.2.6 Study Drug Compliance**

Study drug compliance will be summarized based on the Safety Set, and will be calculated as:  $100 \times [1 - (\text{total number of days of study drug interruption in this open-label study}) / (\text{duration of study drug exposure in days in his open-label study})]$ . A study drug interruption on a given day is defined as an interruption of any study drug on that day. For subjects who enroll in another qualified Vertex study and resume participation in this study, time spent in the other study will be excluded.

Percentage of study drug compliance will be summarized based on the Safety Set. Percentage of study drug compliance will be summarized descriptively by the number of subjects (n), mean,

SD, median, min, and max. It will also be summarized in categories: <80% and  $\geq 80\%$  using frequency tables.

### **9.2.7        Important Protocol Deviations**

An important protocol deviation (IPD) is a deviation that may significantly affect the completeness, accuracy, or reliability of the study data or that may significantly affect a subject's rights, safety, or well-being. A protocol deviation review team will categorize IPDs according to the Protocol Deviation Plan during the study.

IPDs during this open-label study will be summarized descriptively based on the Safety Set. Additionally, IPDs will be provided in an individual subject data listing.

## **9.3           Safety Analysis**

The primary objective of this study is the evaluation of safety and tolerability of ELX/TEZ/IVA. All safety analyses will be based on the TE Period for subjects in the Safety Set.

The overall long-term safety profile of study drug will be assessed in terms of the following safety and tolerability endpoints:

- Treatment-emergent adverse events (TEAEs)
- Clinical laboratory values
- ECGs
- Vital signs
- Pulse oximetry

Only descriptive analysis of safety will be performed and no statistical testing will be performed.

### **9.3.1        Adverse Events**

AEs will be classified as pretreatment AEs, TEAEs, or post-treatment AEs, defined as follows:

- **Pre-treatment AE:** any AE occurred before the first dose date of study drug in the TE Period. For subjects who were enrolled in another qualified Vertex study before completing this study and resume participation in this study, AEs that started during participation in another qualified Vertex study and were ongoing at the time of Returning Visit will be flagged as pre-treatment AE.
- **TEAE:** any AE that worsened (either in severity or seriousness) or newly developed at or after the first dose date of ELX/TEZ/IVA in the TE Period in this open-label study.
- **Post-treatment AE:** any AE that worsened (either in severity or seriousness) or newly developed after the TE Period.

For AEs with missing or partial start dates, if there is no clear evidence that the AEs started before or after study drug treatment start date in this OLS, then the AEs will be classified as TEAEs.

Details for imputing missing or partial start dates of adverse events are described in [Appendix C](#).

An overview of all TEAEs during TE period will be summarized and include the following categories:

- Number of TEAEs (total number of TEAEs only)
- Subjects with any TEAEs
- Subjects with TEAEs by strongest relationship
- Subjects with TEAEs by maximum severity
- Subjects with TEAEs leading to study drug discontinuation
- Subjects with TEAEs leading to study drug interruption
- Subjects with Grade 3/4/5 TEAEs
- Subjects with related TEAEs
- Subjects with serious TEAEs
- Subjects with related serious TEAEs
- Subjects with TEAE leading to death

The frequency counts and percentages will be presented for the above overview table.

The following summary tables of TEAEs will be presented for overall:

- All TEAEs
- Grade 3/4/5 TEAEs
- TEAEs by strongest relationship
- TEAEs by maximum severity
- TEAEs leading to treatment discontinuation
- TEAEs leading to treatment interruption
- Related TEAEs
- Serious TEAEs
- Related serious TEAEs
- TEAEs leading to death

Summaries will be presented by MedDRA SOC and PT using frequency counts and percentages (i.e., number and percentage of subjects with an event). When summarizing the number and percentages of subjects, subjects with multiple occurrences of the same adverse event will be counted once, and only the maximum severity level will be presented in the severity summaries, and the strongest relationship level in the relationship summaries. Missing severity levels will not be included in the Grade 3/4/5 TEAE summaries; missing relationship will be considered as related and included in the related TEAE and related serious TEAE summaries.

An additional summary table in which the number and percentage of subjects will be presented for TEAEs:

- All TEAEs by PT

All AEs in this OLS, including pre-treatment AEs, TEAEs, and post-treatment AEs, will be presented in an individual subject data listing based on the All Subjects Set. In addition, a listing containing individual subject adverse event data for TEAEs leading to treatment discontinuation, TEAEs leading to treatment interruption, Grade 3/4/5 TEAEs, SAEs and all deaths will be provided. Listings for SAEs and deaths will include a flag indicating the TEAE status.

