### **13.1.2.2    Reporting and Documentation of Serious Adverse Events**

All SAEs that occur after obtaining informed consent and assent (where applicable) through completion of study participation, regardless of causality, will be reported by the investigator to Vertex GPS **within 24 hours of identification**. In addition, all SAEs that occur after the Safety Follow-up Visit and are considered related to study drug(s) will be reported to Vertex GPS **within 24 hours of identification**.

For subjects who depart this study to participate in another qualified Vertex study, SAEs will be collected in the same manner as described for AEs (Section 13.1.1.3).

For SAEs that occur after obtaining informed consent and assent (where applicable) through completion of study participation, the SAE Form will be completed for new/initial events as well

as to report follow-up information on previously reported events. Investigators are asked to report follow-up information as soon as it becomes available to ensure timely reporting to health authorities.

Please send completed SAE Forms to Vertex GPS via:

Email: [REDACTED] (preferred choice)

Fax: [REDACTED]

For technical issues related to submitting the form, contact telephone: [REDACTED]

SAEs that occur after completion of study participation and are considered related to study drug(s) will be recorded on the Vertex Clinical Trial Safety Information Collection Form (hereafter referred to as the “SAE Form”) using a recognized medical term or diagnosis that accurately reflects the event. SAEs will be assessed by the investigator for relationship to the investigational study drug(s) and possible etiologies. On the SAE Form, relationship to study drug(s) will be assessed only as related (includes possibly related) or not related (includes unlikely related), and severity assessment will not be required. For the purposes of study analysis, if the event has not resolved at the end of the study reporting period, it will be documented as ongoing. For purposes of regulatory safety monitoring, the investigator is required to follow the event to resolution and report the outcome to Vertex using the SAE Form.

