## 7.2 Sample Size and Power

The primary objective of the study is the evaluation of the safety of ELX/TEZ/IVA. This is an open-label extension study that will enroll the subjects from parent studies who meet eligibility criteria in this study.

Up to approximately 160 subjects are expected to enroll in this open-label extension study.

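### Ungraded TEAEs are left out of the Grade 3/4/5 summaries while missing causality counts as related, so the reported Grade 3/4/5 rate is a lower bound and an ungraded fatal event can be missing from it

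*SAP*

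**What the plan says.** SAP 9.3.1 gives AE fields with missing values different defaults.

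- Severity and causality, in one sentence: "Missing severity levels will not be included in the Grade 3/4/5 TEAE summaries; missing relationship will be considered as related". The sentence goes on to place the latter events in the tables of related and of related serious events.
- Start date: where nothing clearly shows whether the event began before or after treatment started, "then the AEs will be classified as TEAEs".

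The unit of the tables is the subject, since "subjects with multiple occurrences of the same adverse event will be counted once, and only the maximum severity level will be presented in the severity" tables. The denominator comes from SAP 9.3: "All safety analyses will be based on the TE Period for subjects in the Safety Set". SAP 7.2 gives the expected size: "Up to approximately 160 subjects are expected to enroll in this open-label extension study".

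The overview table in SAP 9.3.1 has separate rows for subjects with Grade 3/4/5 TEAEs, with serious TEAEs and with a TEAE leading to death. Maximum severity is tabulated there and again for elevated transaminases and rash in SAP 9.3.1.1. Neither section mentions a missing category. The protocol's AE analysis section (12.3.4.1) has no rule for missing severity, so the rule arises only in the SAP, which gives no reason for it and no sensitivity analysis.

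**The concern.** For two of the three fields the SAP resolves doubt against the drug: unknown causality becomes related, and an unclear start date becomes treatment-emergent. For severity it resolves doubt the other way. An event without a grade is handled, for the Grade 3/4/5 tables, as if it were not severe.

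The exclusion acts on the numerator alone, so a reader of the Grade 3/4/5 row would take as the rate a figure that is only its floor. Without a missing row in the severity tables, that reader could not tell whether any events had been set aside. The sharpest case is a death: one overview table could count a subject as having a fatal TEAE and not count the same subject as having a TEAE of Grade 3, 4 or 5.

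**Working it through.** The plan states no Grade 3/4/5 rate and no missing-grade rate, so there is no figure to reproduce. The 160 is an enrolment expectation, not a calculated sample size. The check is therefore a bound, a test of direction, and a range under stated assumptions.

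**Inputs**

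- N = subjects in the Safety Set, taken as 160 (SAP 7.2; assumes all who enrol are dosed).
- g = subjects with at least one TEAE graded 3 or higher.
- m = subjects with at least one ungraded TEAE and none graded 3 or higher.
- g and m are not in the documents. The values below are assumptions.

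**Bound**

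- Rate under the SAP rule: g/N.
- Rate if every ungraded TEAE counts as Grade 3 or higher: (g + m)/N.
- The rate with complete grading lies between the two, and the gap is m/N. Each subject in m is worth 1/160 = 0.625 percentage points.

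With g = 16, the SAP rule reports 16/160 = 10.00%:

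| m | Upper bound | Gap (points) |
|---|---|---|
| 0 | 16/160 = 10.00% | 0 |
| 1 | 17/160 = 10.625% | 0.625 |
| 2 | 18/160 = 11.25% | 1.25 |
| 5 | 21/160 = 13.125% | 3.125 |
| 8 | 24/160 = 15.00% | 5.00 |

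**Direction**

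Take two subjects with two TEAEs each, every event severe or not and graded or not: 4^4 = 256 configurations. A subject is undercounted when at least one event is severe and every severe event lacks a grade. That holds in 3^2 − 2^2 = 5 of the 16 patterns per subject. The SAP count therefore equals the true count in 11 × 11 = 121 configurations and is lower in the other 135. It is never higher. These counts establish the sign only; the configurations are not equally likely in practice.

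**Expected size if grades are missing at random**

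Let p be the true share of subjects with a Grade 3 or higher TEAE, with one such event each, and q the share of grades missing. The expected bias is −p × q.

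| p | q = 1% | q = 2% | q = 5% |
|---|---|---|---|
| 5% | −0.05 | −0.10 | −0.25 |
| 10% | −0.10 | −0.20 | −0.50 |
| 20% | −0.20 | −0.40 | −1.00 |

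Entries are percentage points. At p = 10% and q = 5% this is 160 × 0.10 × 0.05 = 0.8 subjects; at p = 20% and q = 5% it is 1.6 subjects.

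**The fatal case**

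Protocol Table 13-1 describes Grade 5 as death related to the event. Table 13-4 uses the fatal outcome when the death is at least possibly related to the event. A TEAE leading to death therefore carries the information that its blank grade would have held. Under the SAP rule it enters the death row and, unless the subject has another TEAE graded 3 or higher, stays out of the Grade 3/4/5 row of the same table.

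**The case against.** The case for leaving the rule alone is reasonable, and much of it stands.

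- Few grades should be missing. Protocol 13.1.1.3 lists severity among the data documented for each AE, and 13.1.1.4 has the investigator grade every serious and nonserious event. This limits the size of the problem but not its direction.
- The rule is disclosed in advance and fits the SAP 9.1 default of not imputing missing data. Nothing in the documents requires severity and causality to share a convention. That is fair, but the result still needs to be labelled as a lower bound.
- The study is descriptive, with no testing, so no comparison or decision rule is affected. This stands.

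Four stronger readings are tempting, and the documents do not support them.

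- A reader might infer that serious or fatal events disappear from the report. They do not. They count among all TEAEs and in the serious and death tables, and they appear in the all-AE listing and the listing of SAEs and deaths. The exclusion names summaries, not listings.
- A reader might take the SAE Form as the source of missing grades, because Protocol 13.1.2.2 says "severity assessment will not be required" on it. That form is additional to the CRF, where the grade is recorded. The sentence also stands in a paragraph that opens with SAEs after completion of study participation, and events starting then fall outside the TE Period.
- A reader might conclude that the published Grade 3/4/5 TEAE rate must be too low overall. The claim concerns this one rule. The start-date default can push the same count up.
- A reader might want every ungraded serious event counted as Grade 3 or higher in the main table. Protocol 13.1.2.1 says that seriousness and severity are different things, so seriousness is a debatable stand-in for a grade.

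**Conclusion.** The point holds as a minor reporting defect. Taken alone, the severity rule makes the Grade 3/4/5 rate a lower bound, with zero or negative bias. The bias is zero if no grade is missing, if the ungraded events are truly Grade 1 or 2, or if each affected subject has another TEAE graded 3 or higher. The possible mismatch between the death row and the Grade 3/4/5 row is a separate inconsistency and does not depend on how often grades are missing elsewhere.

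The cost is 0.625 percentage points per affected subject if the Safety Set holds about 160; a smaller set makes each subject worth more. Under the assumed ranges (true rate 5% to 20%, 1% to 5% of grades missing at random), the expected shortfall is 0.05 to 1.0 points. If severe events were more likely than others to lack a grade, the shortfall would be larger, but it could not exceed m/N. The documents give no missing-grade rate, so the actual size is unknown and may be zero.

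**What to change.** Amend SAP 9.3.1 before database lock, which SAP section 4 allows through a documented amendment:

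1. Query every missing severity grade before lock.
2. Count a fatal TEAE that is still ungraded as Grade 5, so that the death and Grade 3/4/5 rows agree.
3. Add a missing-severity row to the maximum-severity tables, including the elevated-transaminase and rash tables in SAP 9.3.1.1.
4. Keep the main Grade 3/4/5 rate otherwise as planned, and report beside it a sensitivity rate that counts all remaining ungraded TEAEs as Grade 3 or higher.

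The cost is a short change of text, one extra row in a few tables and one extra figure. The Grade 3/4/5 rate may come out slightly less favourable. If no grade is missing, no result changes.

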### **9.3.1.1 Adverse Events of Special Interest**

For this study, elevated transaminases events and rash events, as determined by MedDRA Preferred Terms in [Appendix D](#), are considered as adverse events of special interest. The corresponding AE data will be summarized in terms of frequency counts.

For treatment-emergent elevated transaminases events and rash events, the following categories will be summarized:

- Subjects with events
- Subjects with events by maximum severity
- Subjects with events leading to treatment discontinuation
- Subjects with events leading to treatment interruption
- Subjects with serious events
- Subjects with study drug related serious events
- Subjects with events leading to death
- Duration of events
- Time-to-onset of first event (with the first dose date of ELX/TEZ/IVA in the open-label study as the reference while calculating time-to-onset)

In addition, for treatment-emergent rash events, the above categories will be summarized for the following subgroups:

- Sex (male, female)
- Female subjects with concomitant hormonal therapy (Yes, No)

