#### **Additional notes:**

- If over the course of the study the subject meets the criteria for waiving the contraception requirements, the subject does not need to follow the contraceptive methods listed in Table 11-2.
- If over the course of the study the subject's status changes and the subject does not meet the criteria for waiving the contraception requirements, the subject must begin following the contraceptive methods listed in Table 11-2.
- Male subjects must not donate sperm during the period starting from the first dose of study drug until 90 days after the last dose of study drug.

- Female subjects should not nurse a child during the period starting from the first dose of study drug until 90 days after the last dose of study drug.
- Female partners of male subjects should not plan to become pregnant during the study or within 90 days after the last dose of study drug, with the exception of those who plan to become pregnant by artificial insemination using sperm banked by the male subject before the first dose of study drug or sperm from another source.

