#### **12.3.2.3 Prior and Concomitant Medications**

Medications used will summarized descriptively and categorized as the following:

- **Prior medication:** any medication that was administered within the 56 days before the first dose of study drug in this open-label study. For subjects who enroll in another qualified Vertex study and resume participation in this study, any new or changed medication administered after the Departing Visit and prior to the first dose of study drug after resuming participation in this study will also be considered prior medication.
- **Concomitant medication:** medication continued or newly received during the TE Period in this open-label study.
- **Post-treatment medication:** medication continued or newly received after the TE Period in this open-label study.

A given medication may be classified as a prior medication, a concomitant medication, or a post-treatment medication; both prior and concomitant; both concomitant and post-treatment; or prior, concomitant, and post-treatment. If a medication has a missing or partially missing start/end date or time and if it cannot be determined whether it was taken before initial dosing, concomitantly during the TE Period, or beyond the TE Period, it will be considered in all 3 categories of prior, concomitant, and post-treatment medication.

Prior medications and concomitant medications will be summarized descriptively by Preferred Name based on the Safety Set. Post-treatment medications will be provided separately in an individual subject data listing.

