## 9 STATISTICAL ANALYSIS

### 9.1 General Considerations

The precision standards for reporting safety variables are provided in an internal Biometrics document that specifies the programming rules including the precision for derived variables.

**Continuous variables** will be summarized using the following descriptive summary statistics: the number of subjects (n), mean, SD, median, minimum value (min), and maximum value (max).

**Categorical variables** will be summarized using counts and percentages.

**Baseline value**, unless otherwise specified, will be the most recent non-missing measurement (scheduled or unscheduled) collected before the first dose of ELX/TEZ/IVA in a parent study, as applicable.

**Change (absolute change) from baseline** will be calculated as Post-baseline value – Baseline value.

**Treatment-emergent (TE) Period** will include the time period starting from the date of the first dose of study drug of this open-label study to 28 days after the last dose of the study drug, or to the completion date of study participation (as defined in Section 9.1.5 of study protocol), whichever occurs first.

**Unscheduled visits:** Unscheduled visit measurements will be included in analysis as follows:

- 1) In scheduled visit windows per specified visit windowing rules
- 2) In the derivation of baseline and last on-treatment measurements
- 3) In the derivation of maximum and minimum values during the TE period
- 4) In individual subject data listings as appropriate

**Visit windowing rules:** The analysis visit windows for protocol-defined visits are provided in [Appendix A](#).

**Incomplete/missing data** will not be imputed, unless specified otherwise.

**Outliers:** No formal statistical analyses will be performed to detect or remedy the presence of statistical outliers, unless specified otherwise.

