## **9.2.4 Prior and Concomitant Medications**

Medications will be coded using the World Health Organization-Drug Dictionary and categorized as follows:

- **Prior medication:** any medication that was administered within the 56 days before the first dose of study drug in this open-label study. For subjects who were enrolled in another qualified Vertex study before completing this study and resume participation in this study, any new or changed medication administered after the Departing Visit and prior to the first dose of this study's drug after resuming participation will also be considered as prior medication.
- **Concomitant medication:** medication continued or newly received during the TE Period in this open-label study.
- **Post-treatment medication:** medication continued or newly received after the TE Period in this open-label study.

A given medication may be classified as a prior medication, a concomitant medication, or a post-treatment medication; both prior and concomitant; both concomitant and post-treatment; or prior, concomitant, and post-treatment.

If a medication has a missing or partially missing start/end date or time and if it cannot be determined whether it was taken before initial dosing, concomitantly during the TE Period, or beyond the TE Period, it will be considered in all 3 categories of prior, concomitant, and post-treatment medication. Details for imputing missing or partial start and/or stop dates of medication are described in [Appendix B](#).

Prior medications and concomitant medications will be summarized descriptively by Preferred Name based on the Safety Set by 1) preferred name (PN); and 2) anatomic class (ATC) level 1, ATC level 2, and PN. Post-treatment medications will be provided separately in an individual subject data listing.

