**Table 12-2 Prior, Concomitant, and Post Categorization of a Medication**

Medication Start Date	Medication Stop Date		
	< First Dose Date of Study Drug	≥ First Dose Date and ≤ End Date of TE Period	> End Date of TE Period
< First dose date of study drug	P	PC	PCA
≥ First dose date and ≤ End date of TE period	-	C	CA
> End date of TE period	-	-	A

P: Prior; C: Concomitant; A: Post

Same imputation rule will be implemented for missing and/or partial dates of non-pharmacological treatment/procedure.

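### The rash subgroup by concomitant hormonal therapy counts any use in the treatment-emergent period, including use begun after the rash or stopped before it

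*SAP*

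**What the plan says.** SAP 9.3.1.1 names rash as an event of special interest and repeats every summary category for two rash subgroups. One is sex. The other is "Female subjects with concomitant hormonal therapy (Yes, No"). The categories include severity, interruption, discontinuation, duration and time to onset of the first event. The section gives no date at which hormonal therapy is judged and no list of qualifying drugs.

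The general definition of a concomitant medication is in SAP 9.2.4: "medication continued or newly received during the TE Period in this open-label study". Protocol 12.3.2.3 uses the same definition. Under SAP 9.1 the TE Period runs from the "first dose of study drug of this open-label study to 28 days after the last dose of the study drug", or to completion of participation if that is earlier. Table 12-2 in Appendix B assigns the category by comparing start and stop dates with two points only, the first dose date and the end of the TE Period. If timing cannot be determined, SAP 9.2.4 says of the medication that "it will be considered in all 3 categories of prior, concomitant, and post-treatment medication".

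The outcome occupies the same window. SAP 9.3.1 takes as treatment-emergent any event that worsened or "newly developed at or after the first dose date of ELX/TEZ/IVA in the TE Period in this open-label study".

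**The concern.** Exposure and outcome are read from the same interval, and nothing requires the exposure to come first. A woman can enter the Yes group because of something she did after her rash. She can also stay there for a therapy she had already stopped when the rash appeared. The time-to-onset row for the Yes group could then include an onset that preceded any hormone use.

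At stake is how one small table is read. It is one of two subgroup splits for rash, and a reader will take it as showing whether rash is more frequent in women using hormonal therapy. If having a rash changes the chance of a later start, or shortens the period in which a start can be counted, a difference can appear where none exists, or a real one can be hidden.

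**Working it through.** The plan states no figure on this point, so there is none to reproduce. The check has two parts.

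**1. Applying the definitions.** Treatment lasts 48 weeks, which is 48 × 7 = 336 days. With 28 further days the TE Period can reach about 336 + 28 = 364 days.

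- A woman has a rash on Day 30, completes treatment, and starts a hormonal product on Day 200. Her start date meets the Table 12-2 condition "≥ First Dose Date and ≤ End Date of TE Period", so she is coded concomitant and falls in Yes, although she was unexposed at onset.
- A woman already on therapy stops on Day 20 and has a rash on Day 150. Her stop date falls in the same interval, so she is also Yes.
- A woman has a rash on Day 30, takes her last dose on Day 40 and starts a hormonal product on Day 200. Her TE Period ends by Day 40 + 28 = Day 68, so she stays in No. Early stopping after a rash therefore removes the opportunity to be counted as a user.

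**2. Size, for illustration.** All inputs are assumptions, because the documents give only the total of up to approximately 160 subjects, not the number of women, the share using hormones, the rash risk or the start rate. Take U = 24 users and N = 56 non-users at first dose, with rash risk p = 8% in both, so the true ratio is 1.00. Let *a* be the share of non-users with rash who start afterwards, and *b* the share of rash-free non-users who start in the TE Period.

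- Yes risk = (Up + aNp) / (U + aNp + bN(1 − p))
- No risk = (1 − a)Np / ((1 − a)Np + (1 − b)N(1 − p))

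Here Up = 1.92, Np = 4.48 and N(1 − p) = 51.52.

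| a | b | Yes | No | Ratio |
|---|---|---|---|---|
| 25% | 0% | 3.04/25.12 = 12.1% | 3.36/54.88 = 6.1% | 1.98 |
| 25% | 10% | 3.04/30.27 = 10.0% | 3.36/49.73 = 6.8% | 1.49 |
| 25% | 20% | 3.04/35.42 = 8.6% | 3.36/44.58 = 7.5% | 1.14 |
| 10% | 0% | 2.37/24.45 = 9.7% | 4.03/55.55 = 7.3% | 1.33 |
| 10% | 10% | 2.37/29.60 = 8.0% | 4.03/50.40 = 8.0% | 1.00 |
| 10% | 20% | 2.37/34.75 = 6.8% | 4.03/45.25 = 8.9% | 0.76 |

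When a = b the ratio stays at 1.00, because numerator and denominator move together. When *a* exceeds *b* it rises above 1, and when *a* is smaller it falls below. With the class fixed at first dose, the expected result is 8% against 8% throughout.

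Small counts matter as well. Suppose 3 of 24 users and 6 of 56 non-users have a rash: 12.5% against 10.7%, ratio 1.17. If one non-user with rash starts therapy afterwards, the table shows 4/25 against 5/55: 16.0% against 9.1%, ratio 1.76.

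**The case against.** The strongest objection is that few women can be affected. Table 11-2 accepts oral, implanted, injected or vaginal hormonal contraceptives only after at least 60 days of successful use before the first dose, and intrauterine devices only after at least 90 days. Protocol 9.5 adds that subjects should not begin new long-term medication, although it says so within the rule on a stable CF regimen. Most users are therefore probably already on therapy at first dose and correctly start in Yes. This stands. It limits the size of the problem but does not change the definition.

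A reader might infer that mid-study hormonal starts are to be expected, because Protocol 11.2.8.1 says of a subject who no longer qualifies for the contraception waiver that "the subject must begin following the contraceptive methods listed in Table 11-2". The documents do not support that step. The table also lists condoms and female barrier methods with no lead-in, whereas a newly begun hormonal method does not meet its own lead-in condition. Starts are possible, not expected.

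A reader might also take the ratio of about 2 as the likely bias, or take any reclassification as bias. Neither follows. The 1.98 requires that no rash-free woman starts therapy, and it rests on 25% × 4.48 = 1.1 women. Starts unrelated to rash and to follow-up leave the ratio at 1.00. The documents give no reason why a rash would prompt a hormonal start.

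Finally, SAP 9.3 excludes statistical testing, and the adverse event listings let rash and medication dates be compared case by case. This also stands, and it is why the point is minor.

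**Conclusion.** The point holds as a flaw of definition. Under the SAP's general rule, which nothing in either document overrides for this subgroup, use after the rash and use stopped before it both count as exposure. That the general rule governs the subgroup is an inference, since SAP 9.3.1.1 does not spell the variable out, but it is the only definition available.

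The effect on the contrast is conditional. Under the assumptions above, a null association appears as a ratio between 0.76 and 1.98, and as 1.00 when starts are unrelated to rash and to length of follow-up. Few women are likely to be involved, but with so few rash cases one woman can visibly shift the result. No error rate or primary conclusion is affected. A reader might infer that a false contrast would carry through to advice on rash and hormonal therapy, but nothing in the documents shows that.

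**What to change.** In SAP 9.3.1.1, define the subgroup as hormonal therapy ongoing at the first dose of study drug in this study, for both numerator and denominator. In addition, flag for each rash event whether hormonal therapy was ongoing on the rash start date, not counting use begun after onset. Present the flag as a description of cases, without a risk comparison, because women without a rash have no matching date. In the same place, state which drugs count as hormonal therapy and how unresolved medication dates are handled.

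The cost is a few sentences and one derived flag, using medication dates already collected and the imputation rules in Appendix B. There is a small downside. A woman who starts after first dose and then develops a rash is classed No, and one who stops before her rash stays Yes. The event-level flag makes both visible. A full comparison by current use would need person-time on and off therapy, which is more than this descriptive table requires.
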